5.2. DAILY LOG

FICHE DE SUM JOURNALIER (topique)

بطاقة متحفية يومية

CE TABLEAU DOIT ETRE COMPLETE CHAQUE JOUR. Lorsqu'il n'y pas d'application de produit, notez "0" dans la colonne "Nombre".
يجب تعبير هذا الجدول يومياً، عدماً لا يكزن هذه تصلح شفهيًّا، تكتب في خانة عدد

En cas d'insomnie et/ou anxiété, il est recommandé de noter la nature, l'intensité, les précédents, d'angoisse, sensations de douleur, la zone, l'intensité (modérée, sévère, très sévère) et la durée de ces sensations ainsi que le détail d'apparition par rapport à l'application immédiatement après l'application, 5 minutes après etc.

..../M1/M2/M3

6. APPENDICES - ETHICAL REQUIREMENTS AND REGULATORY STANDARDS

6.1. ADVERSE EVENT

6.1.1. Adverse Event (AE)

Any noxious symptom, occurring in a subject taking part in a clinical trial, whether or not this symptom is related to the study or the study product(s) (e.g. flu, headache, abnormal biological analysis...).

6.1.2. Undesirable Effect (UE) / Adverse Reaction (AR)

An **undesirable effect** is defined as an adverse reaction for human health attributable to the normal or reasonably foreseeable use of the cosmetic product(s).

There are 5 levels of imputability: very likely, likely, not clearly attributable, unlikely and excluded (ANSM methodology).

The severity/intensity of undesirable effects/adverse events can be graded on a three-point scale:

- **mild:** discomfort noted, that does not disturb normal daily activities;
- **moderate:** discomfort sufficient to reduce or affect normal daily activities;
- **severe:** inability to work or have normal daily activities.

6.1.3. Serious Adverse Event (SAE) / Serious Undesirable Effect (SUE)

Any event that:

- results in death (note: death is the outcome, not the event);
- is life threatening;
- requires in-patient hospitalization (at least one night) or prolongation of existing hospitalization (does not include hospitalization scheduled before the inclusion);
- results in temporary or permanent functional incapacity or disability;
- is a congenital anomaly;
- is considered like by the investigator.

6.1.4. Documentation

All concomitant treatments are reported in the CRF; only those started after the beginning of the study are reported in the study report.

All Undesirable Effects are reported in the CRF and the study report.

If it requires the temporary or definitive termination of the study product, the need for a corrective treatment or the withdrawal of the subject, an Adverse Event form is completed.

All SAE/SUE are reported in the CRF and the study report.

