| Objectives | 
Primary objective:
 
 • Evaluate the percentage of repigmentation observed one month after the end of three months of treatment measured on an objective layer by image analysis; 
Secondary objectives: Evaluate:
 
 • the percentage of repigmentation observed after one, two and three months of treatment measured on an objective layer by image analysis; • the ability of the product to maintain the human body in good condition (cutaneous acceptability) by clinical examination by the dermatologist; • Patient satisfaction using a visual analogue scale from 0 to 10. • The illustrative effect using standardized photographs; • The quantity of product by weighing the tubes. • The occurrence of possible adverse effects. | | | | | | | | | | | | | | | | | | | | | | | | | | | | | | | | | | | | | | | | | | | | | | | | | | | | | | | | | | | | | | | | | | | | | | | | | | | | | | | | | | | | |
|---|--|---------|-----------------|---------|---------|-------|----|----|-------------------|---|---|---|---|---|---|---|---|---|---|---|---|---|--|---|---|---|---|---|---|--|---|---|---|---|---|---|---|---|---|---|---|---|---|---|---|---|---|---|---|---|---|---|---|---|---|---|---|---|---|---|---|---|---|---|-------------------------------|---|---|---|---|---|---|--|----------|---------|---------|---------|---------|-------|--|----------|---|---|---|---|-------|
| | 
 • Study in proof of concept; • Double blind study; • Comparative study, versus placebo in intra-individual; • Three parallel groups testing different dosages / combinations of treatments; • Randomized. | | | | | | | | | | | | | | | | | | | | | | | | | | | | | | | | | | | | | | | | | | | | | | | | | | | | | | | | | | | | | | | | | | | | | | | | | | | | | | | | | | | | |
| Methodology | | | | | | | | | | | | | | | | | | | | | | | | | | | | | | | | | | | | | | | | | | | | | | | | | | | | | | | | | | | | | | | | | | | | | | | | | | | | | | | | | | | | | |

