1.3. STUDY STAGES

BEFORE THE BEGINNING OF THE STUDY

Technician:

- weighs the study products before their use.

Twice a week:

Patients of both groups A and B come to the hospital where the lesions will be exposed with a Quantel 308 excimer lamp that delivers a narrow UVB spectrum centered of a wavelength of around 308nm. This lamp makes it possible to perform phototherapy localized on the target lesion. Fluences will be performed twice a week throughout the duration of the study.

ON D0**Patients:**

- come to the investigation center without having applied any product to the body since the previous evening;
- are informed about the trial objectives, the procedures and the risks of the study with the information sheet;
- sign two copies of the Consent Form.

Dermatologist:

- verifies inclusion and non-inclusion criteria;
- performs a standardized photo of each target lesion;
- traces and identifies the perimeter of each target lesion (1 to 3 on each side) on a tracing sheet (the natural marks such the scars, moles, tattoos or others will be also reported on the tracing sheet in order to easily find the target lesions);
- performs a clinical examination of the skin on the application area;
- asks the subjects about their usual unpleasant sensations;
- explains to the subjects the product application conditions and frequency;
- gives to the subjects:
 - the product to be used according to the instructions in 2.1.2 and 2.2.2,
 - the daily log to write down their possible unpleasant sensations or medications,

ON M1 (last application being done the previous day)**Subjects:**

- return to the hospital with no product applied to the body since the previous evening;
- bring back their daily log;

Dermatologist:

- performs a standardized photo of each target lesion;
- traces and identifies the perimeter of each target lesion (1 to 3 on each side) on a tracing sheet (the natural marks such the scars, moles, tattoos or others will be also reported on the tracing sheet in order to easily find the target lesions);
- performs a clinical examination of the skin on the application area;
- asks the subjects about the unpleasant sensations they felt during the study and assesses the cutaneous acceptability of the study product;
- collection of the concomitant treatments and undesirable effects.

On M2 (the last application being done the previous night):**Subjects:**

- return to the hospital with no product applied to the body since the previous evening;

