6.1.6. Follow-up

When an adverse event linked to the investigational product or the protocol persists at the end of the study, the Investigator ensures that the subject is followed up until total resolution of the event or stabilization of the symptoms without releasing the Sponsor of any obligation or responsibility.

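### Non-serious events not attributed to the cosmetic product have no general duty to be reported as adverse events: lamp reactions in groups A and B (8 patients) and unrelated events in all 12

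*Combined protocol and SAP*

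**What the plan says.** All references are to the combined protocol and SAP.

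- **Adverse event (6.1.1):** any noxious symptom in a participant, "whether or not this symptom is related to the study or the study product(s").
- **Undesirable effect (6.1.2):** a reaction harmful to health ("attributable to the normal or reasonably foreseeable use of the cosmetic product(s"). The lamp is not mentioned. The same section sets five imputability levels, the lowest being unlikely and excluded.
- **Documentation (6.1.4):** "All Undesirable Effects are reported in the CRF and the study report", and "All SAE/SUE are reported in the CRF and the study report". Between these two rules stands a third: if product termination is required, or "the need for a corrective treatment or the withdrawal of the subject, an Adverse Event form is completed". All concomitant treatments also go into the CRF.
- **Visit steps (1.3):** at M1, M2, M3 and M4 the dermatologist's task is "collection of the concomitant treatments and undesirable effects".
- **Follow-up (6.1.6):** this applies "When an adverse event linked to the investigational product or the protocol persists at the end of the study".
- **Synopsis:** a secondary objective is "The occurrence of possible adverse effects". The schedule table has a matching row at every visit. Section 6.1 does not define the term used there.

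**The concern.** The protocol defines an all-cause adverse event and then does not use that definition in any general recording rule. For non-serious events, the duty to report rests on the undesirable effect, and attribution to the product is part of that definition. Causality thus helps decide whether an event is reported, when it should be a field filled in after the event is recorded.

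This matters most in groups A and B. Each patient there has product on one side, placebo on the other, and the excimer lamp on both. Section 2.3 raises the lamp dose until a clear erythema appears, so the lamp is a ready explanation for a local reaction. If a non-serious reaction is put down to the lamp, the text does not require it to appear in the event listing. The within-patient design could show whether reactions are more frequent or worse on the product side, but only if local events are listed by side whatever their presumed cause.

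**Working it through.** **Step 1. Who is affected.** The randomization list (Appendix 5.1) gives group A = IDs 1, 4, 5, 8; group B = IDs 2, 6, 7, 12; group C = IDs 3, 9, 10, 11. The total is 4 + 4 + 4 = 12, which matches the synopsis (minimum of 12, in groups of 4). By sections 1.2.2 and 1.3, only A and B receive the lamp.

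- Lamp-attributed reactions: 4 + 4 = 8 of 12 patients (8/12 = 67%).
- Unrelated non-serious events: these can occur in any group, so 12 of 12.

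**Step 2. What the text requires for each kind of event.**

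| Event | Duty in 6.1.4 to report as an event |
|---|---|
| Serious, any cause | Yes, CRF and report |
| Non-serious, attributed to product | Yes, CRF and report |
| Non-serious, not attributed to product, leading to product termination, corrective treatment or withdrawal | Adverse Event form, if the rule covers it |
| Other non-serious, attributed to lamp | None stated |
| Other non-serious, unrelated | None stated |

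The third row is uncertain. The sentence on the form begins with a pronoun that follows the undesirable-effect sentence, which suggests undesirable effects only. The name of the form suggests any adverse event.

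**Step 3. Consistency with neighbouring text.**

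- 6.1.6 is wider than 6.1.4. It follows up events linked to the protocol, which would include the lamp, but 6.1.4 does not require all such events to be reported in the first place.
- The imputability levels in 6.1.2 make sense only if events are captured before attribution. The undesirable-effect definition in the same section works the other way.
- Three terms are in use: adverse event (6.1), undesirable effect (1.3, 6.1) and adverse effect (synopsis objective and schedule).

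**Step 4. What is captured elsewhere.** Section 2.4 grades erythema, edema, dryness, desquamation, roughness and other signs at D0, M1, M2 and M3, whatever the cause. Section 1.3 adds a skin examination and questions about sensations at M1 to M4. The daily log takes unpleasant sensations and medications. That is three graded post-baseline time points, or four if the M4 examination is counted. The erythema aimed for in 2.3 lasts under 48 hours, so a reaction of that length can begin and end between monthly visits.

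**Step 5. Effect of attribution made blind to side.** Suppose the same fraction f of local reactions is put down to the lamp on each side and not reported. If the expected counts are p on the product side and q on the placebo side, the reported difference is (1 − f)p − (1 − f)q = (1 − f)(p − q). The documents do not give f. At f = 0 nothing is lost; at f = 1 the whole difference disappears from the listing. Under this assumption the ratio of the sides does not change for f below 1, so the loss is of information and does not favour one side.

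**The case against.** The strongest reply is that little would really be lost. Local signs are graded without an attribution filter, sensations are asked about and logged, and section 1.4 lists clinical signs and reported signs among the data analysed. An event needing treatment leaves a trace through the concomitant-treatment record and perhaps the Adverse Event form. Section 6.2 requires every premature exit to be documented with a reason. The imputability scale and the adverse-effects row in the schedule suggest that all events are meant to be collected and then attributed.

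Much of this stands. A reader might infer that lamp reactions would go wholly unrecorded; the documents do not support that. A reader might also infer that the rule works in favour of the product. The study is double blind and the lamp is used on both sides in A and B, so nothing in the text gives the investigator a reason to blame the lamp more often on one side.

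The reply does not remove the point. Graded signs at scheduled visits are not event reports and can miss short reactions between visits. The section 2.4 table as reproduced shows no right/left field, although a figure is missing there and this needs checking. The section 1.4 table gives acceptability only as D28 against D0. If the imputability scale means that all events are captured first, 6.1.4 and 1.3 should say so; as written they say something narrower.

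**Conclusion.** The concern holds in this form: outside the Adverse Event form route, whose scope is unclear, non-serious events not attributed to the product need not be reported as adverse events. It covers lamp-attributed reactions in 8 of 12 patients and unrelated events in 12 of 12. The counts rest on the 12 entries in the randomization list; section 6.2 mentions 10% additional subjects, who do not appear in it.

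The number of events affected cannot be estimated. A reader might multiply patients by lamp sessions (two a week for about 13 weeks gives 8 × 26 = 208 patient-sessions), but that is exposure, and the documents give no event rate to apply to it. Nor can it be said that a planned result would change: section 1.4.2 is descriptive only, and the side-difference formulas in 1.4.1 concern measured values, not events.

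The change should be made. The gap follows from a stated rule, the rule is at odds with 6.1.2 and 6.1.6, and events not captured during the study cannot be reliably recovered afterwards.

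**What to change.** 1. In 6.1.4 and the visit steps of 1.3, state: *All adverse events as defined in 6.1.1, whatever their causality, are recorded in the CRF and listed in the study report, with side (right/left, or not applicable), relation to product and relation to lamp.*
2. Use one term with one scope in the synopsis objectives, the schedule table, 1.3 and 6.1, so that documentation (6.1.4) is at least as wide as follow-up (6.1.6). State which events the Adverse Event form covers.
3. After unblinding, list local events by product side, placebo side and group.
4. Say where the transient erythema intended under 2.3 is captured, for example in the lamp session record or the 2.4 grading, so that it is not logged as an adverse event at every session.

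The cost is a few sentences, some added CRF fields (the CRF itself is not in the documents) and some extra recording in 12 patients. Without item 4 the burden in groups A and B could be considerable. The change concerns recording and listing only and leaves treatment as it is.

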6.1.5. Notification

The investigator declares to the Sponsor, by e-mail, the occurrence of adverse reactions according to their severity and their unexpectedness (according to the investigator's advice).

All SAE/SUE are transmitted by e-mail to the Sponsor without delay, at the latest 24 hours after knowledge of their occurrence.

A SAE/SUE declaration form signed by a physician is sent, within 48 hours, by e-mail with acknowledgement of receipt.

6.1.6. Follow-up

When an adverse event linked to the investigational product or the protocol persists at the end of the study, the Investigator ensures that the subject is followed up until total resolution of the event or stabilization of the symptoms without releasing the Sponsor of any obligation or responsibility.

6.1.7. Occurrence of pregnancy

The occurrence of a pregnancy (reported or diagnosed) after inclusion in the study is considered as an intercurrent event not related to the study product(s) nor the protocol and induces the immediate dropping out of the subject. Any pregnancy that occurs during the study period is reported by e-mail to the Sponsor within 24 hours following its discovering.

A follow-up is done according to the current internal procedures until the completion/termination of the pregnancy or its interruption.

6.2. PREMATURE TERMINATION OF SUBJECT PARTICIPATION

In compliance with the Helsinki Declaration (1964) and its successive updates, subjects have the right to exit from the study at any time and for any motive.

The investigator can also interrupt the subject participation in the study prematurely in the case of a disease occurrence, a pregnancy or the occurrence of an adverse reaction.

The Sponsor can demand that any subject be excluded from the study for major infringements to the protocol, for administrative reasons or any other motive however this would need to be clearly documented with a rationale as to why.

Nevertheless, premature removal of a high percentage of subjects from the study can make it difficult or impossible to interpret. Consequently, any premature exit without valid motives should be avoided as much as possible and is carefully documented in the case report form, the final report and, if necessary, in the Adverse Event form.

Every premature exit must be classified under one of the following headings:

- presence of a non-inclusion criteria;
- Undesirable Effect / Adverse Event occurrence;
- Serious Adverse Event / Serious Adverse Effect occurrence;
- withdrawal of consent;
- lost to follow-up;
- appearance of non-inclusion criteria;
- non-adherence to the protocol;
- other reason.

No replacement is foreseen as 10% additional subjects are planned to be included in the study.

6.3. CONFIDENTIALITY AND GENERAL DATA PROTECTION REGULATION

In this study, DermScan processes personal data of subjects on behalf of the Sponsor, in accordance with the rules on the protection of personal data. For this purpose, EUROFINS DermScan/Pharmascan limits the collection and use of personal data to that which is needed for analysis and control purposes, by insuring their security and integrity and by guaranteeing their confidentiality.

DermScan makes sure beforehand and throughout the duration of the data-processing:

- of the compliance with the obligations of the applicable data protection law,
- to inform subjects of their personal data-processing after obtaining their consent,

- to implement and maintain appropriate technical and organisational measures.

An identification code is attributed to each subject for the purpose to keep his/her identity confidential. This code consists of: the first two letters/first letter of the subject's name and the first letter of his/her first name.

According to Article 14 of GDPR, the concerned subject must be informed of the identity and the contact details of the Controller and, where applicable, of the controller's representative. However, considering the objective of the study, to avoid any bias in the investigational product evaluation, the identity of the Sponsor is not revealed to the subject participating.

6.4. DATA COLLECTION AND VALIDATION

The staff in charge of the study (doctors, technicians, ...) collects the data in the CRF and on computer support. The simple data entry is carried out from the observation books by a designated operator (s), without any interpretation, in MS EXCEL specific databases.

Then the Project Manager or his assistant checks the coherence of the computer data with those present in the documents of the study. It also checks the formulas used in the EXCEL spreadsheet (calculation formulas, data ranges, etc.).

The consistency of the data coming directly from the measurement software is also verified and validated by the Project Manager or his assistant.

When all the notebooks are entered and all the checks are done, the database is frozen.

The personnel in charge of the study collects data to a computerized data base.

If applicable, the Project Manager or assistant checks the double data entry by comparing both databases.

Then the coherence of the whole data set is checked as well as formulas used in the EXCEL tables (calculation formulas, selected data...).

When all the controls are done, the database is locked.

6.5. QUALITY MANAGEMENT

In order to ensure that the clinical trials are in compliance with the Sponsor's requirement, EUROFINS Dermscan/Pharmascan has implemented a quality management system which has been certified ISO 9001: 2015. This quality assurance system includes Good Clinical Practices (GCP) and regulation requirements.

Each study report is subjected to a quality inspection by a member of the EUROFINS Dermscan/Pharmascan Proofreading Committee. The proofreader is chosen because he(she) is not involved in the audited study. The inspection of the study report allows to confirm that the results reflect exactly the study raw data and that the study fulfils any standard and regulatory requirements.

A certificate of quality inspection signed by the person who checked the report is enclosed in each study.

6.6. ARCHIVES OF STUDY DOCUMENTS
